Secondary Outcome Measures: Evoked Pain will be assessed using instrumented algometry. The mechanical pain threshold (MPT) technique will use a pressure algometer (Force Ten FDX, Wagner Instruments, Greenwich, CT). A pressure algometer is a manually operated force gauge calibrated in kilograms (kg) that administers focal pressure to an area of the body for the purpose of evoking pain or tenderness. The most sensitive point on the quadriceps muscle will be located via palpation and marked for testing. The examiner will apply pressure to the specified point at a rate of 1 kg/sec until the non-noxious pressure turns to pain. The subject will be instructed to indicate the change by saying "pain" at the point when the pressure turns to pain. Each measurement will be performed four times and the average of the four scores will be recorded in kg of force.

Quantitative Sensory Testing (QST): QST is a set of noninvasive tests used to assess pain perception. QST relies on the assessment of an individual's response to external stimuli applied using a stimulus modality (e.g.; pressure and/or temperature), and reflects the integrity of the corresponding sensory pathways to regulate pain transmission and processing by the central nervous system. We will be using QST methods to measure the participants' pain sensitivity and their ability modulate pain perception using endogenous inhibitory pathways.

The QST Protocol will include the following tests: temporal summation, pressure pain threshold and conditioned pain modulation.

Temporal Summation

- 1. A single punctate stimulus using a 6.65 level, 300g force Tactile Semmes-Weinstein monofilament (Fabrication Enterprises, White Plains, NY) will be delivered to the left intermetacarpal space (contralateral side), followed by a VAS pain rating.
- 2. A series of 10 repeated punctate stimuli within a 1cm² site @ 1-Hz will be delivered to the same space as the single stimulus, followed by peak pain rating (VAS).
- 3. Wind-up ratio will be calculated as peak pain (#2) ÷ single pain (#1).

Pressure Pain Threshold (PPT)

Pressure will be applied to the midpoint of the right (ipsilateral) trapezius muscle using a rubber-tipped algometer (Algomed Computerized Pressure Algometer, Medoc Advanced Medical Systems, USA, Durham, NC). The pressure will be increased at a constant rate of 30 kPA per second until the participant indicates the onset of pain (when the sensation of pressure turns to pain). At that point, the test stimulus will be immediately removed. The procedure will then be repeated for a second and third trial, slightly relocating the test applicator tip between each trial to avoid skin irritation. The amount of applied pressure will be recorded at the moment the subject indicates the onset of pain for each trial. The three values will be averaged and recorded as the pressure pain threshold (PPT).

Conditioned Pain Modulation (CPM)

The CPM assessment will include the application of two stimuli:

Test Stimulus (Pressure Pain). Pressure applied to the midpoint of the tibialis anterior (TA) muscle using the algometer and parameters previously described in the PPT test.

Conditioning Stimulus (Cold-pressor Pain). Participants will be instructed to immerse their hand up to the wrist into a cold-water bath maintained at a constant temperature of 12°C by a refrigerated water circulator, and constantly circulated to prevent warming around the hand.

The test stimulus (pressure pain) will be applied to the left TA muscle. Participants will then be instructed to immerse their right (contralateral) hand in the cold-water bath, with fingers splayed, to begin the conditioning stimulus, maintaining their hand in the water bath for as long as they can tolerate for a maximum of one minute. After thirty seconds of hand immersion, subjects will be asked to rate their pain intensity from the immersed hand using a verbal pain scale (0-100). With the participant's hand still immersed in the cold bath, the test stimulus will be repeated on the TA muscle. The subject will be instructed to remove their hand after one minute of immersion, and a final test stimulus will be immediately delivered at the same anatomical site (TA). If the subject chooses to remove their hand prior to 60 seconds of immersion, the final test stimulus (PPT) will be administered to the TA at that point.

Maximal Voluntary Isometric Contraction (MVIC) will be measured using the Biodex System 4 Pro (Biodex Medical Systems, Inc., Shirley, NY). MVIC is the maximum voluntary force produced during a static muscle contraction and is a test of leg muscle function. Subjects will be seated with their dominant leg placed in 60° of knee flexion. Each subject will perform three maximal voluntary isometric actions held for 5 seconds. The maximum of the three values will be recorded as peak torque in Newton-meters (N-m).

The Timed Stair Climbing Test (TSCT). To assess physical function and pain with movement, participants will complete a timed stair climb test at baseline and again at follow-up to evaluate functional recovery. Participants will be timed as they ascend (up) and descend (down) a flight of 10 stairs. After completing the trial, the participant will be asked to rate their level of perceived exertion (CR-10 Borg Scale) and level of perceived pain with movement (VAS).

Participants will complete a series of self-report questionnaires to identify their level of anxiety and fear-avoidant behavior patterns prior to completing the experimental injury protocol. The **Fear of Pain Questionnaire** (FPQ-9) is a 9-item, 5-point rating scale to quantify fear of specific situations that normally produce pain.²⁹ The **Pain Catastrophizing Scale** (PCS) is a 13-item, 5-point rating scale used to assess different thoughts that may be associated with experiencing pain.³⁸ The **Pain Anxiety Symptom Scale** (PASS-20) is a 20 item, 5-point rating scale that assesses 4 theoretically distinct components of pain-related anxiety including cognitive anxiety, fear of pain, escape/avoidance behavior, and physiological anxiety.³⁹ The **Pittsburgh Sleep Quality Index** (PSQI) is a self-report questionnaire that assesses sleep quality over a 1-month time interval. The measure consists of 19 individual items, creating 7 components that produce one global score, and takes 5–10 minutes to complete.

Participants will be informed during the consenting period, both in writing on the consent form and verbally, that participants will likely experience soreness and stiffness within the exercised muscles after completing the exercise protocol. We postulate that participants will likely experience some level of heightened fear and anxiety (pain-related or other) in the 10-day wash-in phase of the investigational test article before they undergo the experimental exercise protocol and recovery phase. We feel this will be quantifiable on the self-reported psychological questionnaires that the participants will complete before and after the experimental protocol.

Data Management & Analysis

All information and data collected will be stored in locked filing cabinets or in computers with security passwords and accessed only by members of the research team. This process facilitates

data entry and collection, allows for participants to complete self-report questionnaires, and offers optimal security for collecting research-related information. The proposed Data Management will be housed within the Human Performance Laboratory and a secure webbased platform approved by UF (e.g. Redcap) will be used.

Outcome measures will be analyzed using a two-way ANOVA with repeated measures (between-group; within-time) or distribution free test (e.g Friedmans) as indicated by data distribution. Statistical significance will be set at p<0.05. If significant interactions occur, the Tukey post-hoc test will be used to reveal where the differences occur. We will calculate effect sizes and estimates of precision for all outcomes. All data analyses will be performed using SPSS® for Windows 16.0 (SPSS, Inc., Chicago, IL).

A **Data and Safety Monitoring Plan** will consist of two components: (1) overseeing participant safety and data monitoring, and (2) performance of monitoring. Since this project is viewed as low potential risk, all key personnel will perform all data and safety monitoring on an as needed basis.

7. Possible Benefits:

There is no known direct benefit from participating in this study. Study participants have the option of being paid for their time performing research related duties or they may choose to receive extra credit for a course they are currently taking and that may or may not be considered a benefit. There are no other obvious benefits to the study participant.

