Cannabidiol (CBD) is one of more than 100 cannabinoids found in the Cannabis Sativa L. or hemp plant. Hemp-derived CBD does not contain any psychoactive ingredients unlike other cannabis products such as $\Delta 9$ -tetrahydrocannabinol (THC). CBD is manufactured and distributed in a variety of ways including isolate, and broad/full spectrum formulations. CBD isolates contain pure CBD (99.9%) and are tasteless and odorless, while broad and full spectrum products contain hemp-extracts that contain CBD (~4%), and very low levels of THC (broad spectrum 0%, full spectrum <0.3%), along with all naturally occurring cannabinoids, terpenes and essential oils from the plant extract. As a constituent, CBD is the same regardless of where it originates; the main difference is in the presence and concentrations of other compounds in the end-product. CBD does not cause intoxication or make you feel euphoric or "high". As a result, many physically-active Americans, including prominent professional athletes, have reported pain relieving effects of CBD that can reduce or eliminate the use of nonsteroidal anti-inflammatory drugs (NSAIDs) for activity-related pain with minimal to no side effects. Long-term use of over the counter (OTC) medications, including NSAIDs, can pose a significant health risk, coupled with the rise in dependence on opioid medications has resulted in the deaths of tens of thousands of Americans annually and over 300,000 deaths during the past decade.^{2,3} Consequently, many consumers of CBD-related products view them as alternatives to NSAIDs for treating such ailments as musculoskeletal and neuropathic pain, anxiety and insomnia, with little to no knowledge or evidence as to best practices regarding dose or method of administration. The sale of CBD and CBD related products is poorly regulated even as the hemp industry is rapidly growing. As of 2016, consumer CBD related sales totaled \$262.2 million, and is estimated to reach \$1.8-billion by 2022.4 A 2019 CBD market report predicts that the industry will reach \$22-billion in the near future.⁵ The widespread use of CBD has gotten far ahead of the research to support the health-related claims that are being made by manufacturers. Therefore, scientific exploration and validation is necessary.

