Inclusion Criteria: a) male and female adults between the ages of 18-35 years and b) English speaking, and c) both female and male subjects must be currently practicing acceptable methods of birth control, such as abstinence, and methods of contraception (barriers, oral, patch or other prophylactic methods).

Exclusion Criteria: (a) use of cannabis products on a regular basis OR positive urine test for cannabis, (b) history of seizure disorder (self or family), traumatic brain injury, liver, kidney, or cardiovascular disease, (c) current medical condition that would prevent the participant from performing strenuous resistance exercise, (d) weight lifting for the lower extremities (legs) more than twice a week, (e) currently experiencing pain in the hips, leg, or knee region, (f) pregnancy, lactating or positive urine pregnancy test, (g) known allergy to CBD, coconut/sesame oil, or tree nuts (coconut).

If the participant self-reports that they are currently using tobacco products or a nutritional/dietary supplement, or if they take prescription anti-depressant/anxiety medications, the participant may continue to use the product(s) but they must be on a stable dose at least 3 months prior to randomization as well as during the 15-day study trial period. Also, if the participant is currently using OTC anti-inflammatory medication (e.g., Advil, Aleve, Aspirin) on a regular basis, we will ask that they stop taking the medication at least 7 days before randomization and refrain from using the product during their participation in the study trial.

Investigational Product & Dosing Schedule

Participants will be provided a 30mL bottle with a syringe dropper on day 1 with instructions to ingest the solution orally using a sublingual route of administration (0.5 cc ~1/2 dropper) twice per day (BID) 12 hours apart (morning and evening) at the prescribed daily dosages: Vehicle-control (0mg/30mL hemp extract = no hemp extract), and active Dose (2000mg/30mL hemp extract = 67mg/day). The sublingual route of administration allows the product to be absorbed directly into venous circulation, and thus bypasses the liver and eliminates the consequences of first pass metabolism; ultimately increasing its bio-availability. The bioavailability of CBD administered orally (including sublingual) is estimated to be 13-19% and its half-life estimated to be around 18-32 hours. 35,36

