SunFlora (St. Petersburg, FL) has been selected as the supplier for the investigational test article. SunFlora is a third-party tested hemp-derived product manufacturing company.

SunFlora is dedicated to producing high quality hemp-derived products formulated to be safely used by the public and are manufactured in accordance with the Food and Drug Administration (FDA) Current Good Manufacturing Practices (cGMP) for Dietary Supplements, 21 CFR Part 111. Their hemp derived products are assessed multiple times at production process control points throughout the manufacturing process. Dietary ingredients used in the manufacturing process are accompanied by certificates of analyses (CoAs) confirming their identity and specifications. All finished products are tested to ensure they meet specifications prior to being released for distribution. The label and all labeling satisfy FDA requirements found under 21 CFR 101. Medium chain triglyceride-based mixing agent blended with coconut oil will be used as the vehicle-control. The addition of the hemp extract to the mixing agent will not change the physical properties of the liquid, and thus will be indistinguishable from the vehicle-control.

Experimental Procedures and Timeline

Recruitment: Participants will respond to advertisements posted around UF campus and on CANVAS sites. Candidates who respond to the advertisements will be contacted by phone for a pre-screen interview to determine if he/she meets the entry criteria. (refer to phone screen for detailed information). Any information collected during the screen will be discarded. If the candidate meets the eligibility criteria, he/she will be sent the informed consent document electronically to read over and familiarize themselves with the protocol. Participants will be instructed not to sign the consent document until they arrive for their 1st visit. Participants will be required to report to the Sports Medicine & Human Performance Research Laboratory for six scheduled visits.

Physical Discomforts and Intervention Risks:

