- 2. Participant is unwilling to continue in the study.
- 3. Lack of compliance with protocol.
- 4. Investigator or study sponsor stops the study for any reason.
- 5. Participant becomes pregnant.
- 6. Participant is enrolled in error or lost to follow-up (lost to follow-up will be defined as a subject failing to attend planned study visits or failure to respond to contacts by study personnel after documented 2 attempts).

*Potential Side Effects and/or Adverse Events (AEs):

- Feelings of anxiety (nervousness, restlessness or being tense, feelings of danger, panic, or dread), paranoia, or negative mood (depression or suicidal thoughts), or paranoia.
- 2. Poor quality of sleep (persistent insomnia).
- 3. Feelings of extreme fatigue, sleepiness or drowsiness.
- 4. Feelings of nausea (upset stomach, vomiting or gastro-intestinal (GI) distress (e.g. diarrhea).
- 5. Change in or loss of appetite.
- 6. Feelings of light-headedness or dizziness.
- 7. Visual disturbances such as blurry/double vision or dilated pupils.
- 8. Hypotension, hypertension, tachycardia, heart palpitations, syncope or dyspnea.
- 9. Development of a skin rash with redness and itching.
- 10. Loss of muscle coordination (clumsiness)
- 11. Muscle spasms

Visit 1 (Consenting, screening, randomization and test product distribution, Day 1)

Participants will be consented. Consenting will be performed by one of the co-investigators in a private room. The following procedures will be performed: urine sample for pregnancy (females) and toxicology screen (presence of cannabinoids), a brief physical exam (including vital signs: measurements for height, weight, pulse, blood pressure and body temperature), obtaining a thorough medical and psychiatric history, including a review of past medical history, concomitant medications, inclusion/exclusion criteria and potential contraindications, assessment of the oral cavity and sublingual area to rule out any active lesions or abnormalities (bleeding, sores, ulcers, abscesses, etc.). If any lesions are found to be present, the research assistant will document the findings and follow up with a consultation phone call with the study physician to determine next steps. The study participant may choose to be excluded from participation or wait until the condition fully resolves. If the participant continues with the study protocol, follow up oral assessments will be repeated at visits 2 through 6.

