Results of urine screening for pregnancy and toxicology (presence of cannabinoids) will be available and assessed during the first visit. If the urine test (pregnancy or cannabinoids) comes back positive, the participant will be excluded from the study. The participant will complete several psychological questionnaires (FPQ-9, PCS, PASS-20, PSQI, & LEFS), followed by tests for muscle soreness and quantitative sensory testing (QST). Each participant will be provided a detailed safety monitoring checklist of side effects and/or adverse reactions that they may potentially experience from ingesting the investigational product. Participants will then be instructed on how to perform their own passive surveillance for identifying these side effects/adverse events and what to do if they experience any of them between study visits while they are ingesting the investigational test article (Days 1 through 10). Participants will be instructed to maintain current activity levels and not to initiate a resistance-training or weightloss program for the duration of the study. Participants will then be randomly assigned to an experimental group and instructed on how to ingest the investigational test article (or placebo) and dosing procedures, which will be dispensed in a quantity to last for the next 15 days. Each participant will be provided a daily log chart to record their daily CBD doses for compliance and monitoring purposes. A pre-exercise visit will be scheduled. Each subject will receive \$10 for completion of the test session.

During the passive surveillance period (Days 1 through 10) participants will be instructed to contact the PI ([name]) if they experience any of the side effects/adverse events from the checklist provided at the baseline visit. [name]/[name] will then contact the study physician ([name]) for consultation. The side effects/adverse reactions will be triaged as mild, moderate or severe, and a determination will be made as to whether the side effect/adverse reaction is due to the investigational product or some other circumstance (e.g. food poisoning). If the event is determined to be due to the investigational test article and graded moderate to severe by the study physician, the participant will then be instructed to stop participation and seek medical care by their primary physician or hospital. Any participant that reports a serious adverse event will be followed to full resolution.

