Visit 2 (Pre-exercise measurements and exercise protocol, Day 11)

Participants will be assessed actively (including vital signs) at each subsequent visit by study personnel using the side effects/adverse events checklist. Each participant will be read each side effect/adverse reaction from the checklist and instructed to self-report as yes (go) or no (no go). For participants who continue in the study, the following procedures will be performed: completion of psychological questionnaires (FPQ-9, PCS, PASS-20, PSQI, & LEFS), followed by tests of muscle soreness, quantitative sensory testing (QST), the timed stair climbing test (TSCT) and isometric strength measures to evaluate leg function. Participants will then undergo a standardized single bout of eccentric resistance exercise to the dominant quadriceps muscle. An isokinetic dynamometer (Biodex System 4 Pro, Biodex Medical Systems, Inc., Shirley, NY) will be used for the eccentric exercise protocol. Each participant will then perform five sets of twenty-five repetitions. Exercise will be performed using concentric (meaning shortening of muscles during contraction) and eccentric (lengthening of the muscle while still developing tension). The angular velocity will be set at 60°/sec for concentric and 90°/sec for eccentric actions. Participants will be given a three-minute rest period between sets. Each subject will receive \$15 for completing the test session.

Visit 3, 4, & 5 (Follow-up measurements @ 24, 48, & 72-hr post-exercise, Day 12, 13, & 14)
The following procedures will be performed: completion of psychological questionnaires (PCS & LEFS), followed by tests of muscle soreness and leg function testing (TSCT and isometric strength measures). Participants will receive \$5 for completing visits 3, 4 and 5.

Visit 6 (Follow-up measurements @ 96-hr post-exercise, Day 15)

The following procedures will be performed: completion of psychological questionnaires (FPQ-9, PCS, PASS-20, PSQI, & LEFS), followed by tests of muscle soreness, QST, and leg function testing (TSCT and isometric strength measures). At the end of the session each participant will be asked if they thought they were taking the active CBD product or placebo. Participants will receive \$10 for completing visit 6.

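### The request to avoid OTC anti-inflammatories reaches only current regular users, and the protocol describes no record of analgesic use after Visit 1, although soreness is induced and is a primary outcome

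*Combined protocol and SAP*

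**What the plan says.** The restriction is in section 6, Study Population. It applies "if the participant is currently using OTC anti-inflammatory medication (e.g., Advil, Aleve, Aspirin) on a regular basis". Those participants are asked to stop at least 7 days before randomization and to "refrain from using the product during their participation in the study trial". The stable-dose rule in the same paragraph covers tobacco, supplements and prescription antidepressant or anxiety medication, but not analgesics. The general conduct instruction at Visit 1 concerns activity level, resistance training and weight loss.

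Medication is reviewed once, at Visit 1, "including a review of past medical history, concomitant medications, inclusion/exclusion criteria and potential contraindications". The Safety Monitoring section ties the same review to the first visit. After that, the protocol describes two ways of collecting information from participants about their conduct and side effects:

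- The log: "Each participant will be provided a daily log chart to record their daily CBD doses".
- The checklist: "Participants will be assessed actively (including vital signs) at each subsequent visit by study personnel using the side effects/adverse events checklist".

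The phone screen leaves no record either: "Any information collected during the screen will be discarded".

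The Primary Outcome Measures are self-reported soreness (its duration and its peak intensity) and disability on the LEFS. The Data Management & Analysis section does not mention analgesic use.

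**The concern.** The study injures a muscle on purpose and tells participants at consent to expect soreness and stiffness. An OTC analgesic is an ordinary response to that. The protocol already treats these drugs as a threat to the outcome, since regular users must stop 7 days before randomization and abstain during the trial. A first dose taken on Day 12 by someone who is not a regular user acts on the same outcome, yet the text neither discourages nor records it.

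Use need not be equal in the two arms. The Background says that physically active people "have reported pain relieving effects of CBD that can reduce or eliminate the use of nonsteroidal anti-inflammatory drugs (NSAIDs) for activity-related pain". That is a report, not evidence about this trial, but it is the mechanism the study has in mind. If CBD relieves soreness, vehicle participants would be sorer, might take more analgesics, and would then look more like the CBD arm.

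The stated purpose is preliminary data for a larger trial, with effect sizes for every outcome. At stake is whether those effect sizes could be somewhat too small, with no described data to show whether analgesic use differed by arm.

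**Working it through.** The plan states no figure on this point, so there is none to reproduce. The check is mainly a reading of the text.

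**Step 1. Who is restricted.** Current regular users of OTC anti-inflammatories are. Occasional users and non-users are not. Analgesics that are not anti-inflammatories, and prescription analgesics, are not mentioned for anyone.

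**Step 2. Where use could be recorded.**

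| Source in the protocol | Covers analgesic use after Visit 1? |
|---|---|
| Phone screen | No; before enrolment, and discarded |
| Visit 1 medication review | No; Day 1 only |
| Daily log | Described for CBD doses |
| Checklist at Visits 2 to 6 and the 1-week call | No; 11 symptom items, 0 on medication or muscle soreness |
| Visit 2 procedures (before exercise) | None listed |
| Visits 3 to 6 procedures (24, 48, 72, 96 hours) | None listed |

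Use prompted by the induced soreness can be asked about only at the four post-exercise visits, 3 to 6. The count is 0 of 4. Visit 2 could capture only use before the exercise.

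**Step 3. Which outcomes could move.**

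- Soreness duration and daily soreness ratings: relief on a sore day lowers the rating and can bring forward the apparent end of soreness.
- Daily LEFS ratings: relief can improve reported function on that day.
- Peak soreness: less exposed. It is the highest rating of worst soreness over the past 24 hours, so soreness bad enough to prompt a dose is still captured even if the dose then relieves it.
- The LEFS peak summary: no claim. Items are scored so that 4 means no difficulty, and the highest score is recorded. As written, that is best function, which relief on sore days would hardly change.

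**Step 4. Direction.** Let k be vehicle-arm users minus CBD-arm users, and e the reduction in a rating per user, in SD. With 15 per arm, and ignoring any change in the SD:

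loss in the contrast = (k / 15) × e

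If k = 0, the loss is 0. If CBD has no effect, nothing drives k systematically away from 0, so no false difference is expected on average.

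**Step 5. Illustration only.** The documents give no usage rate, analgesic effect, SD or target difference. All of the following are assumptions: k from 0 to 4, e from 0.5 to 1.0 SD, and a true standardized difference d of 0.80.

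| k | e | Loss (SD) | Observed d |
|---|---|---|---|
| 0 | any | 0 | 0.80 |
| 1 | 0.5 | (1/15) × 0.5 = 0.033 | 0.77 |
| 2 | 1.0 | (2/15) × 1.0 = 0.133 | 0.67 |
| 4 | 1.0 | (4/15) × 1.0 = 0.267 | 0.53 |

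For comparison, the approximate standard error of d = 0.80 with 15 per arm is √(2/15 + 0.80²/(2 × 30)) = √0.144 = 0.379. The 95% half-width is 1.96 × 0.379 = 0.74. Every loss in the table lies inside it.

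**The case against.** **The instruction may exist elsewhere.** The consent form, phone screen and log form are not in the reviewed text, and any of them could carry a wider request or a medication question. This stands as a limit: the point is that the protocol text is silent, not that no such instruction exists. If one does, a cross-reference settles the matter.

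**Sampling error dominates.** In an exploratory study with 15 per arm, a half-width of 0.74 SD exceeds any loss in the illustration. This stands, and it is a main reason for rating the point minor.

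**Recording changes no estimate.** If the primary analysis stays on observed ratings, a record of use adds only description. That is true of the record. The wider request is what can reduce use, and letting participants take relief when they need it weakens it somewhat. The record is still worth having, because use by arm cannot be reliably reconstructed later.

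**Stronger readings that the documents do not support.**

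- A reader might infer that unrecorded analgesic use could produce a spurious CBD benefit. The mechanism runs towards no difference, and needs CBD to work in the first place.
- A reader might infer that every primary outcome is diluted alike. Step 3 shows that peak soreness is partly protected and that the LEFS peak summary, as defined, gives no basis for the claim.
- A reader might infer that a later trial would be badly mis-sized. Under the assumptions above, a two-sample t-test at 80% power and two-sided 0.05 needs 26 per arm at d = 0.80 and 57 at d = 0.53. The larger figure needs four excess users, each gaining more from an analgesic (1.0 SD) than the whole assumed CBD effect (0.80 SD). With one excess user at 0.5 SD the requirement is 28. None of these inputs is in the documents.

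**Conclusion.** The concern holds as a minor one. The rule on OTC anti-inflammatories is too narrow for a trial that induces soreness and then measures it, and the protocol text describes no means of learning who took analgesics on Days 11 to 15. If sorer vehicle participants took more, the contrasts in soreness duration and in daily soreness and LEFS ratings would be attenuated, and peak soreness less so. The size cannot be estimated from the documents; the 0 to 0.27 SD range above is arithmetic on assumed inputs.

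The conclusion on attenuation rests on two conditions that the documents do not establish: that CBD reduces soreness, and that analgesic use follows soreness. The gap in restriction and recording rests only on the protocol text.

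**What to change.** 1. **Widen the request.** Under Study Population, ask all participants to avoid any analgesic or anti-inflammatory through Day 15. State that anyone who needs relief may take it, logs it and stays in the study, so that use does not trigger the third stopping criterion, "Lack of compliance with protocol". Without that sentence the wider request could lead to withdrawal of the sorest participants.
2. **Record use.** Add an analgesic line (name, date, time) to the existing daily log. Check it at Visit 2 for use before the exercise and at Visits 3 to 6 for use after it.
3. **Report it.** Give the number of users and the time of first use by arm, and keep the primary analysis on observed ratings. Any analysis that excludes or censors data after first use should be optional and exploratory, because first use itself depends on soreness.

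**Cost:** an amended request, one log line, one question at each of five existing visits and a short descriptive entry in the results. No extra visits or participants are needed. The downside is slight added burden for participants and staff, and a request to forgo routine relief unless it is needed.
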